**Duration:**

Treatment may continue indefinitely until one of the following criteria applies: 1) unacceptable toxicity (including DLT in cycle 1); 2) progressive disease; or 3) participant withdrawal or removal.

**Primary Objective:**

To determine the safety and tolerability of cabozantinib (XL184) as a single agent in solid tumor participants with HIV infection and to determine the maximal tolerated dose (MTD) in this participant population.

**Secondary Objectives:**

1. To investigate possible pharmacokinetic interactions between cabozantinib and antiretroviral therapy in persons with HIV infection.
2. To investigate the effects of therapy on participant immune status and HIV viral load.
3. To preliminarily assess objective response rates associated with treatment for commonly represented tumors.

## PROTOCOL SCHEMA

Dose Level	Dose Escalation Schedule		
	Dose of Cabozantinib (XL184)*		
	Stratum A ART Regimens Including Drugs that Inhibit CYP3A4 A (mg/day)	Stratum B ART Regimens Including Drugs that Induce CYP3A4 B (mg/day)	Stratum C All Other ART Regimens C (mg/day)
Level -2	-	20	20
Level -1	20 mg every other day	40	40
Level 1	20	60	60
Level 2	40	100	-
Level 3	60	-	-

**\* Cabozantinib (XL184): must be taken on an empty stomach. Participants must be instructed not to eat for at least 2 hours before and at least 1 hour after taking cabozantinib. Participants should be instructed to take their cabozantinib dose at approximately the same time every day. If a participant misses a dose, the dose may be taken later only if it is within 12 hours of when the missed dose should have been taken. The missed dose should not be made up if it is within 12 hours of the next scheduled dose.**

A Stratum A: Participants taking either ritonavir-boosted or cobicistat-boosted ART regimens

B Stratum B: Participants taking either efavirenz or etravirine-based ART regimens.

C Stratum C: Participants taking any antiretrovirals not specified in Stratum A or B as of November 30, 2012, and participants who are not taking an ART regimen.

**Note: If an antiretroviral is FDA-approved after November 30, 2012, consult the Study Pharmacologist for Stratum designation).**

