## 5.0 TREATMENT PLAN

### 5.1 Agent Administration

Treatment will be administered on an outpatient basis. Reported adverse events and potential risks are described in [Section 7.0](#). Appropriate dose modifications are described in [Section 6.0](#). No investigational or commercial agents or therapies other than those described below may be administered with the intent to treat the participant's malignancy.

Cabozantinib will be administered orally as once daily doses continuously over 28 day cycles in each of three treatment strata in participant cohorts as detailed in the table below. The starting dose in each treatment Stratum will be Dose Level 1. Dose escalation will proceed in participant cohorts within each Stratum according to the scheme described in [Section 5.2](#).

**NOTES: The participant will be requested to maintain a medication diary of each dose of medication. The medication diary will be returned to clinic staff at the end of each course.**

**The site will be required to document study agent return by participant in source documents. Non-compliance with study agent administration should be noted at the time of diary collection and the participant should be instructed again regarding dosing instructions.**

**Missed cabozantinib doses will NOT be made up. Participants who have missed a dose should wait until the next scheduled dose to resume therapy.**

For Stratum A, one dose de-escalation cohort (Dose Level -1) will be permitted for excessive toxicity observed at the initial (Dose Level 1) cohort. For Stratum B and Stratum C, two dose de-escalation cohorts (up to Dose Level -2) will be permitted for toxicity observed at initial cohorts.

For participants treated on Stratum A no dose escalation will proceed beyond Dose Level 3 (60 mg). For participants treated on Stratum B, no dose escalation will proceed beyond Dose Level 2 (100 mg). For participants treated on Stratum C, no dose escalation will proceed beyond Dose Level 1.

Dose Escalation Schedule			
Dose Level	Dose of Cabozantinib (XL184)*		
	Stratum A ART Regimens Including Drugs that Inhibit CYP3A4 A (mg/day)	Stratum B ART Regimens Including Drugs that Induce CYP3A4 B (mg/day)	Stratum C All Other ART Regimens C (mg/day)
Level -2	-	20	20
Level -1	20 mg every other day	40	40
Level 1	20	60	60
Level 2	40	100	-
Level 3	60	-	-

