## 10.0 BIOMARKER, CORRELATIVE, AND SPECIAL STUDIES

### 10.1 Biomarker Studies

10.1.1 To investigate possible pharmacokinetic interactions between cabozantinib and antiretroviral therapy in persons with HIV infection.

This study will enroll participants with HIV infection across three Strata based on current antiretroviral regimen (Ritonavir or Cobicistat (CYP3A4 inhibitor)-containing HAART [**Stratum A**]; Efavirenz or Etravirine (CYP3A4 inducer)-containing HAART [**Stratum B**]; and Others [**Stratum C**]). The study therefore provides an opportunity to evaluate possible pharmacokinetic interactions between cabozantinib and antiretroviral therapies.

Pharmacokinetic (PK) sampling studies are proposed for all participating participants on the study to assess cabozantinib pharmacokinetics (total and possibly unbound concentrations of parent drug and relevant metabolites). In addition, when feasible, samples will be requested from the participant at the time of disease progression and in the event of DLT or other persistent and severe toxicity. Evaluations will occur at steady-state (Cycle 1, Days 22/23) given the long half-life of the drug ( $91.3 \pm 33.3$  hr) which is not conducive to a comprehensive assessment after a single dose. If a participant misses a dose of cabozantinib during Cycle 1 prior to Cycle 1 Days 22/23 and will continue on treatment, [name] should be contacted to determine the optimal timing of the PK collection, which may no longer occur on Cycle 1 Days 22/23. Since cabozantinib is to be administered continuously, the adjustment may occur in the date of the collection but not the 8 samples to be obtained. The exact timing will depend on the duration of interruption and proximity to Cycle 1 Days 22/23. In some circumstances, the PK collection may be waived due to difficulties in rescheduling the PK.

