**To permit pharmacokinetic sampling studies, AM dosing is required during the first cycle of therapy.** Blood samples will be collected prior to the initial AM cabozantinib dose and at 4 hours post-dose on Cycle 1 Day 1. Blood sampling for steady-state PK determinations will be collected during the dosing interval at pre-dose (Cycle 1, Day 22), 0.5, 1, 2, 4, 6, 8, and 24 hr (Cycle 1, Day 23). For the optional samples that are to be obtained at the time of disease progression or in the event of toxicity, a blood sample should be drawn as close as possible to the time of the event with documentation of the last cabozantinib dose administered. For each sample, at least 6 mL of whole blood will be collected in tubes or Vacutainers™ containing EDTA as an anticoagulant, kept on ice, and centrifuged within 30 min to isolate plasma. Plasma will be frozen in two to three aliquots immediately and stored at  $-70^{\circ}\text{C}$  (or less) protected from light for later analysis by the Analytical Pharmacology Core Laboratory at the Sidney Kimmel Comprehensive Cancer Center at Johns Hopkins University under the direction of [name] (See [Appendix IV](#) Pharmacokinetic (PK) Specimen Collection, Preparation and Shipping Instructions).

Samples will be measured using liquid chromatography/tandem mass spectrometric (LC/MS/MS) method in the Analytical Pharmacology Core

Laboratory at the Sidney Kimmel Comprehensive Cancer Center (SKCCC) at Johns Hopkins. Relevant individual PK parameters will be estimated using non-compartmental or compartmental PK methods with the software WinNonlin. For each Stratum, the pharmacokinetic variables will be tabulated and descriptive statistics (e.g., geometric means and coefficients of variation) calculated for each dose level. Pharmacokinetic parameters (i.e.,  $T_{1/2}$ ,  $Cl$ , and AUC) will be compared across relevant antiretroviral therapies using nonparametric statistical testing techniques. Correlations with toxicity and efficacy will be explored using nonparametric statistical testing techniques. Significance for comparisons will be at the  $p<0.05$  level.

10.1.2 To investigate the effects of therapy on participant immune status and HIV viral load.

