### 10.2.1.1 Collection of specimens

This study will be performed on all participating participants as described in [Appendix IV](#), Pharmacokinetic (PK) Specimen Collection, Preparation and Shipping Instructions. Samples will be collected prior to the initial cabozantinib dose and at 4 hours post-dose on Cycle 1 Day 1. Steady-state PK samples will be collected during the dosing interval at pre-dose (Cycle 1, Day 22), 0.5, 1, 2, 4, 6, 8, and 24 hr (Cycle 1, Day 23). Day 22 and Day 23 PK samples may be collected  $\pm$  1 day. If a participant misses a dose of cabozantinib during Cycle 1 prior to Cycle 1 Days 22/23 and will continue on treatment, [name] should be contacted to determine the optimal timing of the PK collection, which may no longer occur on Cycle 1 Days 22/23. In addition, when feasible, samples will be requested from the participant at the time of disease progression and in the event of DLT or other persistent and severe toxicity.

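### The Day 22/23 PK schedule is written for daily dosing and is not adapted to every-other-day dosing at Stratum A Level -1, where it falls on an off-dose day and covers half the interval

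*Combined protocol and SAP*

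**What the plan says.** The Protocol Schema and the dose tables in Sections 5.1 and 6.0 give Stratum A Level -1 as "20 mg every other day". Section 5.1 opens this level only after toxicity at the starting level ("one dose de-escalation cohort (Dose Level -1) will be permitted for excessive toxicity"). Section 6.0 also makes it the lowest step for individual dose reduction in Stratum A, and it allows reductions during Cycle 1.

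The general regimen text has no exception for this level: "Cabozantinib will be administered orally as once daily doses continuously over 28 day cycles". The medication diary in Appendix VIII likewise assumes a dose every morning.

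Dosing starts on Cycle 1 Day 1 (Section 10.1.1: "Blood samples will be collected prior to the initial AM cabozantinib dose and at 4 hours post-dose on Cycle 1 Day 1"). The steady-state series is "collected during the dosing interval at pre-dose (Cycle 1, Day 22), 0.5, 1, 2, 4, 6, 8, and 24 hr", the last sample falling on Day 23. Section 10.2.1.1, Appendix I (footnote i) and Appendix IV repeat it. The Appendix IV table asks for a pre-dose sample on Day 22 and another on Day 23, which fits only daily dosing.

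There is some flexibility. Section 10.2.1.1 ("Day 22 and Day 23 PK samples may be collected") and Appendix IV allow one day either side. After a missed dose the date can be reset with the pharmacology laboratory, but Section 10.1.1 limits this: "the adjustment may occur in the date of the collection but not the 8 samples to be obtained".

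Sections 10.1.1 and 12.4 allow non-compartmental or compartmental estimation, tabulate PK by dose level, and compare half-life, clearance and AUC across antiretroviral therapies at the 0.05 level.

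**The concern.** Every-other-day dosing from Day 1 falls on odd days: 1, 3, ..., 19, 21, 23. A site that follows the schedule as written takes the Day 22 pre-dose sample 24 h after the last dose, with no dose to follow. The next seven samples then trace a decline, with no absorption peak. If the site starts on Day 21 or 23 instead, the series begins at a dose but stops halfway to the next one.

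Interaction with antiretroviral therapy is the first secondary objective, and Stratum A is the stratum in which inhibition is expected to raise exposure. A clearance estimate biased upward at this level works against that expected effect and could mask it. Samples not taken in Cycle 1 cannot be recovered at the analysis stage.

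**Working it through.** **Inputs.** Dose 20 mg, interval 48 h (Protocol Schema). Sampling times 0, 0.5, 1, 2, 4, 6, 8 and 24 h (Section 10.1.1). Half-life 91.3 ± 33.3 h, so 58.0, 91.3 and 124.6 h are used (Sections 2.4 and 10.1.1). Steady-state clearance 4.2 L/h, steady-state AUC 41.6 mcg·h/mL at 175 mg daily, and tablet tmax 4 h (Section 2.4).

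**Step 1: the documents' own clearance.** Cl = dose/AUC over the dosing interval = 175/41.6 = 4.21 L/h, matching the stated 4.2 L/h. This is the calculation that needs the whole interval.

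**Step 2: share of the interval covered, closed form.** Ignoring absorption time, let r = 2^(-24/half-life). The first 24 h after a dose hold 1/(1+r) of the 48 h AUC, and the second 24 h hold r/(1+r). At 91.3 h, r = 0.833, giving 0.545 and 0.455.

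**Step 3: the same with absorption.** A one-compartment oral model by superposition was used: 20 mg on Days 1, 3, 5 and so on, Cl 4.2 L/h, absorption rate set to give tmax 4 h, and a trapezoidal AUC over the eight protocol times. At 91.3 h, the AUC over the full 48 h from Day 21 is 4.67 mg·h/L.

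| Series start | AUC0-24 (mg·h/L) | Share of AUC0-48 | 20/AUC0-24 (L/h) | Ratio to 4.2 | 10/AUC0-24 (L/h) | Ratio to 4.2 |
|---|---|---|---|---|---|---|
| Day 21 | 2.54 | 54% | 7.88 | 1.88 | 3.94 | 0.94 |
| Day 22 | 2.14 | 46% | 9.35 | 2.23 | 4.67 | 1.11 |
| Day 23 | 2.55 | 55% | 7.84 | 1.87 | 3.92 | 0.93 |

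From Day 22 the highest value is the first sample, so no peak is seen.

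**Step 4: range over half-lives of 58.0 to 124.6 h.** The Day 22 start captures 43-47%, and the Day 21 or 23 start 53-57%. Dividing the full 20 mg dose by AUC0-24 gives clearance 1.77 to 2.31 times the true value. Dividing the mean daily dose of 10 mg gives 0.88 to 1.15 times.

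**Step 5: control.** The same eight times on 20 mg daily give 4.28 L/h at 91.3 h, 2% above 4.2. The schedule suits daily dosing, so the mismatch is specific to this level.

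**Step 6: after the change proposed below.** With samples at 0, 0.5, 1, 2, 4, 6, 8 and 48 h from Day 21, the linear trapezoidal AUC at 91.3 h is 4.70, so Cl = 20/4.70 = 4.25 L/h. Over the half-life range it is 4.15 to 4.42 L/h, from 1% below to 5% above the true 4.2. The upper end reflects steady state not being quite reached at the longest half-life.

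**The case against.** A reader might infer that AUC and clearance at Level -1 are bound to be wrong by about two-fold. The documents do not support that, for four reasons.

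- The day is not fixed. The one-day window already permits a start on Day 21 or 23, both dosing days.
- No formula for clearance is mandated. Compartmental analysis is allowed, Appendix IV has sites record actual sample times and the previous and current dose times, and a fit to that history does not need a full 48 h interval.
- AUC0-24 is close to average daily AUC, which is half of AUC0-48. At 91.3 h it is 2 × 0.457 = 0.91 times that value from Day 22, and 2 × 0.543 = 1.09 times from Day 21. Section 2.4 reports an AUC coefficient of variation of 40-43% for the tablet, so this bias is modest beside the between-subject spread. The two-fold error needs an analyst to divide a full 20 mg dose by a half-interval AUC.
- Level -1 is a contingency. Section 5.3.1.3 reports a 38% AUC rise with a strong CYP3A4 inhibitor, so 20 mg with a booster may behave like 20 × 1.38 = 27.6 mg, under half the 60 mg standard dose. The documents give no DLT rate for boosted participants, so no probability that the level opens is claimed here.

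All four stand, and they limit the size of the point. They do not remove it. Nothing tells sites to use the window for a planned off-dose day, the window does not lengthen the 24 h span, the rescheduling rule concerns missed doses and keeps the eight samples unchanged, and neither a compartmental model nor mean-daily-dose scaling is specified for this level.

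**Conclusion.** The point holds as a mismatch between one dose level and the sampling plan. Followed as written, the schedule gives an off-dose-day series holding about 46% of AUC0-48 with no absorption peak. A dosing-day start raises the share to 54-55%. The resulting clearance error runs from about 15% or less (mean daily dose) to a factor of 1.8 to 2.3 (full dose over AUC0-24), depending on an analysis choice that the plan leaves open.

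These figures assume a one-compartment shape and the half-life from the cited phase I study. If boosting lengthens the half-life, the captured share moves toward 50% from either start day. The clearance value cancels from the AUC shares, and the error ratios are relative to it.

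The issue arises only if a Level -1 cohort opens or a Stratum A participant is reduced to that level before the Cycle 1 series. It affects the secondary PK objective. Escalation and MTD decisions rest on toxicity alone and are untouched. It is a minor but easily corrected gap.

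**What to change.** **Sampling.** Add a footnote in Appendix IV, cross-referenced from Sections 10.1.1 and 10.2.1.1 and Appendix I footnote i. For participants on every-other-day dosing, the steady-state series starts on a dosing day (Day 21 when dosing began on Day 1 without interruption), and the last sample moves from 24 h to just before the next dose (48 h, Day 23). Day 21 lies within the existing window. A Day 23 start would not work, because its 48 h sample would fall on Day 25, outside Day 23 ± 1. A participant reduced to this level during Cycle 1 may have different dosing days and may not be at steady state, so timing should be agreed with the pharmacology laboratory, extending the route already used for missed doses.

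**Analysis.** Add one sentence to Sections 10.1.1 and 12.4: AUC and clearance at this level use the actual 48 h interval, or a compartmental model with recorded dose times, and exposure is compared across strata as average daily AUC.

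**Consistency.** The once-daily wording in Section 5.1 and the diary text should be reconciled with the Level -1 entry in the dose tables. No change of dose is proposed.

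**Cost.** A footnote and a sentence. The number of samples (eight) and of PK visits is unchanged. The 24 h sample is given up at this level, so the decline between 8 and 48 h rests on two points.

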## LIST OF ABBREVIATIONS

ACSR .....	AIDS and Cancer Specimen Resource
ADM .....	AIDS-defining Malignancies
AdvantageEDC SM .....	AMC Internet Data Entry System
AE .....	Adverse Event
AIDS .....	Acquired Immunodeficiency Syndrome
ALT .....	Alanine Aminotransferase
AMC .....	AIDS Malignancy Consortium
AML .....	Acute Myelocytic Leukemia
ANC .....	Absolute Neutrophil Count
APC .....	Analytical Pharmacology Core
ART .....	Antiretroviral Therapy
AST .....	Aspartate Transaminase
AUC .....	Area under the Curve
B-HCG .....	Beta-Human Chorionic Gonadotropin
BP .....	Blood Pressure
BUN .....	Blood Urea Nitrogen
cART .....	Combined Antiretroviral Therapy
CAEPR .....	Comprehensive Adverse Events and Potential Risks
CBC .....	Complete Blood Count
CDC .....	Centers for Disease Control and Prevention
CDUS .....	Clinical Data Update System
CHF .....	Congestive Heart Failure
cPR .....	Confirmed Partial Response
CR .....	Complete Response
CRF .....	Case Report Form
CT .....	Computed Tomography Scan
CTCAE .....	Common Terminology Criteria for Adverse Event reporting
CTEP .....	Cancer Therapy Evaluation Program
CTEP-AERS .....	CTEP-Adverse Event Reporting System
CTMS .....	Clinical Trials Monitoring Service
Oral DARF .....	Oral Drug Accountability Record Form
DBP .....	Diastolic Blood Pressure
DCTD .....	Division of Cancer Treatment and Diagnosis
DL .....	Dosing Level
DLT .....	Dose-Limiting Toxicity
DSMB .....	Data Safety Monitoring Board
DTC .....	Differentiated Thyroid Cancer

DVT	Deep Vein Thrombosis
ECG	Electrocardiogram
EIACD	Enzyme-Inducing Anti-Convulsant Drug
ELISA	Enzyme Linked Immunosorbent Assay
FDA	Food and Drug Administration
FDG-PET	Fluorodeoxyglucose-Positron Emission Tomography
GABA	$\gamma$ -aminobutyric acid
GB	Glioblastoma
GCSF	Granulocyte Colony-Stimulating Factor
GEJ	Gastroesophageal Junction
GI	Gastrointestinal
HAART	Highly Active Antiretroviral therapy
HCC	Hepatocellular Carcinoma
HGF	Hepatocyte Growth Factor
HIV	Human Immunodeficiency Virus
HR	Hazard Ratio
IAM	Identity and Access Management
IB	Investigator's Brochure
IDB	Investigational Drug Branch
IDF	Investigator Data Form
IEC	Independent Ethics Committee
IND	Investigational New Drug Application
INR	International Normalized Ratio
IRB	Institutional Review Board
kg	kilogram
KS	Kaposi sarcoma
LDH	Lactate Dehydrogenase
LFT	Liver Function Test
LLN	Lower Limit of Normal
LMWH	Low Molecular Weight Heparin
mcL	microliter
MDS	Myelodysplastic Syndrome
mg	milligram
mL	milliliter
MRI	Magnetic Resonance Imaging
MTC	Medullary Thyroid Cancer
MTD	Maximum Tolerated Dose
NADC	Non-AIDS Defining Cancer
NCI	National Cancer Institute
NOAEL	No-Observable-Adverse-Event-Levels

NSAIDS	Nonsteroidal Anti-Inflammatory Drugs
NSCLC	Non-Small-Cell Lung Cancer
NYHA	New York Heart Association
OAOP	Online Agent Order Processing
ODMC	Operations and Data Management Center
OHAM	Office of HIV AIDS Malignancy
ONJ	Osteonecrosis of the Jaw
OTC	Over the Counter
PCNSL	Primary Central Nervous System Lymphoma
PD	Progressive Disease
PE	Pulmonary Embolism
PFS	Progression-Free Survival
PIB	Powder-in-Bottle
PIO	Protocol Information Office
PMB	Pharmaceutical Management Branch
PO	Per oral [by mouth]
PK	Pharmacokinetic
PPE	Palmar-Plantar Erythrodysesthesia
PPI	Proton Pump Inhibitor
PR	Partial Response
PT	Prothrombin Time
PTT	Partial Thromboplastin Time
QD	Daily
RCC	Renal Cell Carcinoma
RPLS	Reversible Posterior Leukoencephalopathy Syndrome
RT	Radiation Therapy
RTK	Receptor Tyrosine Kinase
SAE	Serious Adverse Event
SBP	Systolic Blood Pressure
SCLC	Small Cell Lung Cancer
SD	Stable Disease
SF	Scatter Factor
SOC	System Organ Class
SPEER	Specific Protocol Exception to Expedited Reporting
TdP	Torsades de Pointes
TFT	Thyroid Function Test
TIA	Transient Ischemic Attack
TMZ	Temozolomide
TSH	Thyroid-Stimulating Hormone
UA	Urinalysis

ULN .....Upper Limit of Normal  
UPCR .....Urine Protein/Urine Creatinine Ratio  
µM.....micromolar

## **1.0 OBJECTIVES**

### **1.1 Primary Objectives**

To determine the safety and tolerability of cabozantinib (XL184) as a single agent in solid tumor participants with HIV infection and to determine the maximal tolerated dose (MTD) in this participant population.

### **1.2 Secondary Objectives**

- 1.2.1 To investigate possible pharmacokinetic interactions between cabozantinib and antiretroviral therapy in persons with HIV infection.
- 1.2.2 To investigate the effects of therapy on participant immune status and HIV viral load.
- 1.2.3 To preliminarily assess objective response rates associated with treatment for commonly represented tumors.

## **2.0 BACKGROUND**

This is a phase I, dose escalation study of cabozantinib (XL184) for advanced solid tumors in persons with HIV infection.

### **2.1 HIV-Associated Malignancies**

In addition to the AIDS-defining malignancies (ADMs), which include Kaposi sarcoma, non-Hodgkin's lymphoma and cervical cancer, several non-AIDS defining cancers (NADCs) are seen in excess in HIV positive populations, including anal cancer, head and neck cancer, hepatocellular carcinoma, and lung cancer (Patel *et al.*, 2008). NADCs are increasing in prevalence and as a result have become a major cause of morbidity and mortality in persons with HIV-infection (Shiels *et al.*, 2011). In an era of active biological therapies for cancer, surprisingly little evidence for treatment of ADMs and NADCs exists for HIV infected individuals, as persons with HIV infection and cancer have historically been excluded from many cancer trials (Persad *et al.*, 2008; Weiss *et al.*, 2011). Given this currently underserved patient population, the tolerability of exciting novel agents, particularly agents that are likely to have activity in both ADMs and NADCs, should be confirmed early on in an effort to broaden inclusion of this patient population in future large scale national and international studies.

